## 8.1 DOSING AND ADMINISTRATION OF STUDY MEDICATION

## 8.1.1 Dispensing Directions

Dispensing instruction will be provided in Pharmacy Instructions in the study manual.

## 8.1.2 Dosing Information

BVD-523 is to be taken twice daily orally with at least 8 ounces of water for 21 days, at 12-hour  $\pm$  2 hour intervals. The study medication should be taken at the same time each day on an empty stomach, i.e., fasting (30-60 minutes before food or 2 hours after food). A patient that is observed to vomit an intact capsule after dosing in the clinic during the PK measurements may receive a substitute dose of drug. However, patients should be instructed NOT to take a substitute capsule if vomiting occurs after self-dosing at home. Missed doses should be skipped and not taken as a double dose at the next dosing timepoint.

Since this is a second-in-human study relatively little human toxicity has thus far been experienced. Therefore, dose modifications for any toxicity seen will be developed as data are accrued. However, patients experiencing DLT or unacceptable toxicity will have their treatment interrupted until the toxicity returns to  $\leq$  Grade 1 or pre-treatment baseline. BVD-523 treatment may then be re-initiated at the next lower dose level where the safety profile has previously been established, or between the dose level yielding unacceptable toxicity and the previous dose level, aligning with capsule dose availability. Such dose adjustments will be done in consultation with the Investigators and Medical Monitor of the study.

#### 8.1.3 Dosing Instructions for the Study Participants

Patients will be instructed to take their study medication twice daily at 12-hour  $\pm 2$  hour intervals. The study medication should be taken with at least 8 ounces water at the same time each day on an empty stomach (30-60 minutes before food or 2 hours after food).

#### Drug Storage

Information will be provided in the study manual.

#### Drug Accountability

The investigator or study staff will verify the integrity of the clinical trial supplies (storage conditions, correct amount received, condition of shipment, kit numbers, etc.) according to Standard Operating Procedures.

The following data will be tracked on the drug accountability log provided by the Sponsor, and recorded in the eCRF:

- Date received
- Lot number
- Date dispensed
- Patient number

Records of study medication (used, lost, destroyed, and returned containers, individual capsules) should be made at each patient visit in the eCRF. Drug accountability and reconciliation will be checked by the site study monitor during site visits and at completion of study treatment.

Unless prohibited by investigational site SOP, used study medication is to be retained until the monitor has verified drug accountability. Once the site monitor has verified drug accountability at the site, any drug remaining in opened dispensing containers will be destroyed. Unused and unopened study medication will be returned to the Sponsor.

## 8.2 **RESCUE MEDICATIONS AND CONCOMITANT TREATMENTS**

All medications administered from 30 days prior to the commencement of study treatment (Day 1) through the end of the treatment period (Day 22) will be recorded on the eCRF. Any changes of dosages of medication will also be noted.

### 8.3 TREATMENT COMPLIANCE

The investigator will dispense the study medication only for use by patients enrolled in the study as described in this protocol. The study medication is not to be used for reasons other than those described in this protocol.

The investigator or other study staff will supervise study drug treatment given in the clinic and instruct the patient on study medication self-administration at Visit 2 (Baseline). Patients will be asked to bring their study medication container with them at each visit and compliance with

protocol-defined study drug intake will be checked by pill count. In case of non-compliance, the patients will be instructed again.

# 9 ADVERSE EVENT MANAGEMENT

## 9.1 DEFINITION OF AN ADVERSE EVENT

An Adverse Event (AE) is defined as any untoward medical occurrence in a patient administered a medicinal product that does not necessarily have a causal relationship with this treatment. An AE can, therefore, be any unfavorable and unintended sign (including an abnormal laboratory finding), symptom, or disease temporally associated with the use of a medicinal (investigational) product, whether or not related to the study (investigational) product. This includes an exacerbation of pre-existing conditions or events, intercurrent illnesses, drug interaction, or the significant worsening of the indication under investigation that is not recorded elsewhere in the eCRF under specific efficacy assessments. Anticipated fluctuations of pre-existing conditions, including the disease under study that does not represent a clinically significant exacerbation or worsening, need not be considered AEs.

It is the responsibility of the investigator to document all AEs that occur during the study. AE information will be elicited by asking the patient a non-leading question, for example, "Have you experienced any new or changed symptoms since we last asked/since your last visit?" AEs should be reported on the appropriate page of the eCRF.

## 9.2 DEFINITION OF A SERIOUS ADVERSE EVENT

A Serious Adverse Event (SAE) is any untoward medical occurrence that occurs at any dose (including after the ICF is signed and prior to dosing) that:

- Results in death
- Is life-threatening (patient is at immediate risk of death from the event as it occurred)
- Requires in-patient hospitalization (formal admission to a hospital for medical reasons) or prolongation of existing hospitalization
- Results in persistent or significant disability/incapacity
- Results in a congenital anomaly/birth defect

Important medical events that may not result in death, are not life-threatening, or do not require hospitalization may be considered SAEs when, based on appropriate medical judgment, they may jeopardize the patient and may require medical or surgical intervention to prevent one of the outcomes listed in this definition. Examples of such events include allergic bronchospasm requiring intensive treatment in an emergency room or at home, blood dyscrasias or convulsions that do not result in in-patient hospitalization, or the development of drug dependency or drug abuse.

Hospitalizations for elective surgery or other medical procedures that are not related to a treatment-emergent AE are not considered SAEs.

Progression of the malignancy under study (including signs and symptoms of progression) should not be reported as an SAE unless the outcome is fatal during the study or within the safety reporting period (see below). If the malignancy has a fatal outcome during the study or

within the safety reporting period, then the event should be reported using the term "disease progression" with a CTCAE severity of Grade 5.

# 9.3 RECORDING OF ADVERSE EVENTS AND SERIOUS ADVERSE EVENTS

Recording and reporting of adverse events should be in accordance with the FDA "Guidance for Industry and Investigators Safety Reporting Requirements for INDs and BA/BE Studies" of December 2012.

Any AE is to be recorded in the eCRF. In order to avoid vague, ambiguous, or colloquial expressions, the AE should be recorded in standard medical terminology rather than the patient's own words. Whenever possible, the investigator should combine signs and symptoms that constitute a single diagnosis.

The existence of an AE may be concluded from a spontaneous report of the patient; from the physical examination; or from special tests, e.g., ECG, laboratory assessments, or other study-specified tests (source of AE).

The reporting period begins from the time that the patient provides informed consent through and including 30 calendar days after the last administration of BVD-523. AEs may occur in the specified follow-up period. Any SAE occurring after the reporting period must be promptly reported if a causal relationship to the investigational drug is suspected. If the patient begins a new anticancer therapy, the safety reporting period ends at the time the new treatment is started, however, death must always be reported when it occurs during the 30-day reporting period irrespective of intervening treatment.

Each AE is to be evaluated for duration, severity, seriousness, and causal relationship to the investigational drug. The action taken and the outcome must also be recorded. In the event that a rash is noted and reported as an AE, the rash should be documented with photographs as soon as it is reported through resolution. Patients must give consent for photographs to be taken.

## 9.4 INTENSITY OF ADVERSE EVENTS

The severity of the AE will be graded according to the NCI CTCAE Grading Scale Version 4.03 (see the NCI CTCAE web page at http://ctep.cancer.gov for details). For AEs not covered by NCI CTCAE, the severity will be characterized as "mild", "moderate", or "severe" according to the following definitions:

- Mild events are usually transient and do not interfere with the patient's daily activities.
- Moderate events introduce a low level of inconvenience or concern to the patient and may interfere with daily activities.
- Severe events interrupt the patient's usual daily activities.

## 9.5 RELATIONSHIP OF ADVERSE EVENTS TO STUDY DRUG

The investigator will make a judgment regarding whether or not the AE was related to study drug, as outlined below, and in accordance with FDA guidance of 2012.

Unrelated	The adverse event is unlikely to have been caused by study drug.
Possibly related	It is unclear whether the adverse event may have been caused by study drug.
Related	The adverse event is likely to have been caused by study drug.

# 9.6 FOLLOW-UP OF ADVERSE EVENTS AND SERIOUS ADVERSE EVENTS

All AEs occurring during the study are to be followed up in accordance with good medical practice until they are resolved, stabilized or judged no longer clinically significant or, if a chronic condition, until fully characterized. Any AEs that are considered drug-related (possibly related, related) must be followed until resolution or until stabilization. Any AE of rash should be documented until resolution with photographs.

# 9.7 POST STUDY ADVERSE EVENTS AND SERIOUS ADVERSE EVENTS

All unresolved AEs should be followed by the investigator until the events are resolved, the patient is lost to follow-up, or the AE is otherwise explained. At the last scheduled visit, the investigator should instruct each patient to report any subsequent event(s) that the patient, or the patient's personal physician, believes might reasonably be related to participation in this study. Prior to the conclusion of the study at the site the investigator should notify the Safety Associate (see Section 9.8) of any death or AE occurring at any time after a patient has discontinued or terminated study participation that may reasonably be related to this study. After study conclusion the investigator should notify BioMed Valley Discoveries, Inc., or their designee, Clinipace Worldwide (CPWW), of any death or AE they are aware of occurring at any time after a patient has discontinued or terminated study Discoveries, Inc., should also be notified if the investigator should become aware of the development of cancer or of a congenital anomaly in a subsequently conceived offspring of a patient that has participated in this study.

## 9.8 REGULATORY ASPECTS OF ADVERSE EVENT REPORTING

Unexpected serious suspected adverse reactions are subject to expedited reporting to FDA. ALL SAEs must be entered into the eCRF within 24 hours of first knowledge of the event by study personnel. It is important that the investigator provide his/her assessment of relationship to study drug at the time of the initial report. Entry of an SAE into the eCRF triggers an automatic alert to the CPWW safety team. Timely notification of an event supersedes the requirement to have all information at the time of the initial report. The following information must be reported on the eCRF SAE report form:

- Protocol number
- Site and/or Investigator number
- Patient number
- Demographic data
- Brief description of the event
- Onset date and time
- Resolution date and time, if the event resolved
- Current status, if event not yet resolved
- Any concomitant treatment and medication
- Investigator's assessment of whether the SAE was related to Investigative product or not
- Outcome of the event if available

The CPWW Safety Associate will contact the site for clarification of data entered onto the eCRF, or to obtain missing information. In the event of questions regarding SAE reporting, the site may contact:

Safety Associate Clinipace Worldwide, Inc. [contact]

BioMed Valley Discoveries, Inc., or their designee CPWW, is responsible for submitting reports of AEs associated with the use of the drug that are both serious and unexpected to FDA according to 21 CFR 312.32 and the draft guidance (2010). All investigators participating in ongoing clinical studies with the study medication will receive copies of these reports for prompt submission to their Institutional Review Board (IRB) or Ethics Committee (EC).

#### 9.8.1 Overdose

No information on treatment of overdose of BVD-523 is currently available. In the event of an overdose, the overdose should be reported as an AE and the Medical Monitor should be notified.

#### 9.8.2 Pregnancies

Pregnancy per se is not considered an AE unless there is cause to believe that the investigational drug may have interfered with the effectiveness of a contraceptive medication. Hospitalization for normal delivery of a healthy newborn should not be considered a SAE.

Each pregnancy in a patient or partner of a patient on BVD-523 must be reported to the Sponsor within 24 hours of learning of its occurrence. If a patient becomes pregnant, study drug administration must be discontinued immediately. The pregnancy should be followed up to determine outcome, including spontaneous or voluntary termination, details of the birth, and the presence or absence of any birth defects, congenital abnormalities, or maternal and/or newborn complications. Follow-up and documentation must occur even if the patient withdraws from the study or the study is completed.

The avoidance of pregnancy or fathering a child is suggested for 3 months following the discontinuation of BVD-523 therapy. No information is currently available regarding the effects of BVD-523 on fertility, gestation or subsequent child development.

Any pregnancy within 3 months post-study should be reported to the study investigator and to CPWW.

# **10 STATISTICAL METHODS**

## **10.1 GENERAL CONSIDERATIONS**

#### 10.1.1 Statistical and Analytical Plans

A formal detailed statistical analysis plan (SAP) will be created prior to the review of any data.

The purpose of this Phase 1/2 dose escalation study is to determine the maximum tolerated dose (MTD), the dose limiting toxicity (DLT), and the recommended Phase 2 dose (RP2D) of orally administered BVD-523 in patients with AML or MDS. Groups of 3–6 patients will be treated at each dose level until the maximum tolerated dose is reached. All patients meeting the eligibility criteria and receiving at least 1 dose of BVD-523 will be evaluable for safety.

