## 7.2 DISCONTINUATION OF INDIVIDUAL PATIENTS

Patients are to be withdrawn from the study for any of the following reasons:

- Withdrawal of informed consent
- Disease progression (at the discretion of the PI)
- Unacceptable toxicity
- Changes in the patient's condition which render the patient unacceptable for further treatment in the judgment of the PI
- At least 3 interruptions of BVD-523 intake of > 7 days each, or 8 consecutive days
- Patient becomes pregnant (withdrawal is required)
- Patient is lost to follow-up

Patients will also to be withdrawn at any time if the Investigator concludes that it would be in the patient's best interest for any reason. Protocol violations do not lead to patient withdrawal unless they constitute a significant risk to the patient's safety.

Patients can voluntarily withdraw from the trial for any reason at any time. They are to be considered withdrawn if they state an intention to withdraw, fail to return for visits, became lost to follow up for any reason, or if any of the following occurs:

- Discovery of patient ineligibility
- Significant errors in treatment compliance of at least three interruptions of 7 days each, any treatment interruption of ≥8 consecutive days, or incomplete dosing for greater than 7 days
- Missed / unscheduled / off-schedule / incomplete / incorrect assessments that result in patients being put at risk.

In Part 1 of the study, patients who withdraw at any time due to unrelated AEs preceding the last visit of Cycle 1 (Day 22) will constitute an early discontinuation and must be replaced in order to ensure proper data accrual for dose escalation decisions. A patient who experiences a DLT in Cycle 1 and withdraws before Day 22 either because of the toxicity or otherwise, will nonetheless have that DLT counted in the assessment of potential cohort expansion and/or dose escalation (Table 3.2).

In Part 2 of the study, patients who withdraw at any time preceding the last visit of Cycle 2 (Day 43) will constitute an early discontinuation and will not be replaced and will be evaluated in the Intent to Treat analysis. If patients withdraw due to progressive disease or AEs, replacement of such patients potentially introduces bias into the study. If a patient withdraws for other reasons, replacement of the patient will be decided by the Safety Monitoring Committee.

The investigator must determine the primary reason for a patient's withdrawal from the study and record this information on the eCRF.

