## **10.2 ANALYSIS DATASETS**

#### **10.2.1** Population to be Analyzed

The safety population will consist of all patients receiving at least 1 dose of study medication.

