#### 10.3.8 Safety Data

All safety summaries will be provided for the Safety population.

Summaries for safety variables (physical examinations, vital signs, clinical laboratory analyses) will be given. All safety variables will be presented in by-patient listings, sorted by site and patient identifier.

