### 5.2 SAFETY

The Safety Population will consist of all subjects receiving at least 1 dose of study drug. Demographic and baseline characteristics will be tabulated for the Safety population. The Safety population will be used for all safety analyses. Safety analyses from Part 1 will be presented overall as well as broken down by dose level. Safety analyses from Part 2 will be presented overall as well as broken down by dose level, specifically at the RP2D dose of 600 mg.

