#### 9.1 PRIMARY ENDPOINT ANALYSIS

As this is a Phase 1/2 study, there is no formal primary efficacy endpoint.

The primary safety endpoints are the DLTs and MTD for BVD-523 administered alone in subjects with AML or MDS (Part 1) and preliminary efficacy (AML/MDS response) of BVD-523 administered at the RP2D dose in subjects with AML or MDS with or without RAS mutant positive disease (Part 2). The MTD and RP2D will be determined based upon the observed DLTs at each dose level as described in the protocol.

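### Protocol 10.1.1 ties safety evaluability to eligibility, against Protocol 10.2.1 and SAP 5.2, and with SAP 5.4 leaves three limited gaps in whose DLT is counted

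*Protocol*

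**What the plan says.** Protocol 10.1.1 closes its paragraph on determining the MTD, DLT and RP2D with "All patients meeting the eligibility criteria and receiving at least 1 dose of BVD-523 will be evaluable for safety".

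The formal definitions omit eligibility. Protocol 10.2.1 has "The safety population will consist of all patients receiving at least 1 dose of study medication" and SAP 5.2 has "The Safety Population will consist of all subjects receiving at least 1 dose of study drug". Protocol 10.3.8 adds "All safety summaries will be provided for the Safety population", and SAP 5.2 adds "The Safety population will be used for all safety analyses". The SAP table list (14.3.1), whose entries are all labelled Part II, puts the DLT tables and the table of doses selected as MTD and RP2D on the Safety Population.

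Protocol 7.2 bears on the point in two ways:
- It lists "Discovery of patient ineligibility" among the events after which a patient is considered withdrawn, so the plan foresees the situation.
- For Part 1 it provides that "A patient who experiences a DLT in Cycle 1 and withdraws before Day 22 either because of the toxicity or otherwise" still has that DLT counted for cohort expansion and dose escalation. It has no equivalent sentence for Part 2.

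On the MTD, SAP 9.1 says "The MTD and RP2D will be determined based upon the observed DLTs at each dose level as described in the protocol". SAP 5.4 instead assigns the Part 1 MTD calculation to the per-protocol (PP) population, which excludes subjects with a major protocol deviation. SAP 8.6 lists inclusion/exclusion breaches as a deviation category, to be graded major or minor before each Part's tables are produced.

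**The concern.** A toxicity seen after dosing is information about the dose whether or not the patient should have been enrolled. A safety definition that depends on eligibility allows a later administrative finding to remove an observed event. Cohorts here hold 3 to 6 patients in Part 1 and up to 20 in Part 2, so one removal can move a count across a decision boundary.

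The eligibility wording stands in the paragraph about MTD and RP2D, and SAP 9.1 refers that decision back to the Protocol. Someone settling whose DLT counts could therefore come to 10.1.1. SAP 5.4 points the same way by a separate route. At stake are the MTD as calculated and reported, and the Part 2 pause on enrolment.

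**Working it through.** The plan states no computed figure on this point to reproduce. The check compares the texts and then shows what one dropped patient does to the counts.

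**Step 1. Who counts, by section**

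| Place | Patients counted | Eligibility condition |
|---|---|---|
| Protocol 10.1.1 | dosed and eligible | yes |
| Protocol 10.2.1, 10.3.8 | at least one dose | no |
| SAP 5.2; DLT and MTD/RP2D tables in SAP 14.3.1 | at least one dose | no |
| SAP 5.4 (Part 1 MTD) | PP population | indirectly, through major deviations |
| Protocol 3.1.4.1, Table 3.2, Section 8 | patients in the dose cohort | silent |
| Protocol 10.1.2 (Part 2 trigger) | patients in a cohort with at least 6 enrolled | silent |

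**Step 2. Which routes are open**

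- *Part 1, DLT in Cycle 1, withdrawn for ineligibility before Day 22.* Closed for escalation. Protocol 7.2 keeps the DLT whatever the reason for withdrawal.
- *Part 1, ineligibility found on or after Day 22.* Open. The retention sentence stops at Day 22, whereas deviation grading (SAP 8.6) and the Part 1 data review (SAP 12.3) can come later.
- *Part 1, ineligibility found but the patient stays on study.* Open. Protocol 7.2 also says that protocol violations lead to withdrawal only if they pose a significant safety risk, and retention applies only to patients who withdraw.
- *Part 2.* Open. There is no retention sentence, and the 33% trigger does not say who is in the numerator or denominator.
- *SAP 5.4.* Open whatever Protocol 7.2 says, because 7.2 governs expansion and escalation, not an MTD calculated on the PP population. SAP 12.3 has the Part 1 analysis feed the MTD discussion. SAP 9.4 has the Part 1 tables follow the MTD. On the second reading the risk is a reported MTD that disagrees with the working one.

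**Step 3. Effect of dropping one DLT patient: d/n becomes (d − 1)/(n − 1)**

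Part 1 rules: escalation stops with more than 1 DLT in 6 or fewer patients, and the MTD requires fewer than 33%.
- 2/6 = 33.3% stops escalation and is not below 33%. It becomes 1/5 = 20.0%, which is one DLT and below 33%.
- If the dropped patient were replaced by one without a DLT, it becomes 1/6 = 16.7%, the row of Table 3.2 that permits escalation. The written replacement rule covers unrelated adverse events only.
- 3/6 = 50.0% becomes 2/5 = 40.0%. The call does not change.

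Part 2 rule: more than 33%, taken literally.

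| Before | After one drop | Trigger still met? |
|---|---|---|
| 7/20 = 35.0% | 6/19 = 31.6% | no |
| 3/8 = 37.5% | 2/7 = 28.6% | no |
| 4/10 = 40.0% | 3/9 = 33.3% | yes |
| 3/7 = 42.9% | 2/6 = 33.3% | yes |

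One removal therefore matters only when the count sits close to the boundary.

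**The case against.** The strongest reply is that 10.1.1 is introductory text and no decision rule uses it. The MTD definition, Table 3.2, Section 8 and the Part 2 trigger all count patients without mentioning safety evaluability. SAP 9.1 leads naturally to Protocol 3.1.3, 3.1.4 and 7.2. Safety summaries are assigned to the dosed population in both documents. The sentence says that all such patients are evaluable, not that only they are. This largely stands. A reader might infer from the sentence's position that 10.1.1 lets any DLT in an ineligible patient be deleted from the Part 1 escalation count. The documents do not support that, because Protocol 7.2 keeps the DLT in the commonest case.

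Two things survive. The eligibility phrase has no function in 10.1.1 unless it restricts. The routes left open in the working are not covered by 7.2.

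A reader might also want a frequency. If 2% to 10% of dosed patients were later found ineligible (an assumption), 1 − (1 − e)^6 gives 11% to 47% of six-patient cohorts containing at least one. That is the chance of an ineligible patient in the cohort, not of a lost DLT or a changed decision. For the 2/6 example, an assumed 33% DLT rate gives the path 1/3 then 1/3 a probability of (3 × 0.33 × 0.67²)² = 0.198. The chance that at least one of the two DLT patients is ineligible is 1 − (1 − e)² = 4% to 19%. The product is about 0.8% to 3.8%, before allowing for 7.2. Both rates are assumed, so neither range is a finding.

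**Conclusion.** The inconsistency is real and its reach is limited. Protocol 10.1.1 conflicts with Protocol 10.2.1 and SAP 5.2. Its consequence is confined to ineligibility found on or after Day 22 or without withdrawal, to Part 2, and to the PP-based MTD in SAP 5.4. The last is the more direct route, because it assigns the MTD calculation explicitly. It also sits badly with a SAP that sends all safety analyses to the dosed population.

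The size is shown by illustration only: 33.3% reading as 20.0% in Part 1, and 35.0% reading as 31.6% in Part 2. Both assume that exactly one DLT patient is dropped and that the count was near the boundary. Nothing in the documents shows that any DLT has been dropped. SAP 5.2 already names a 600 mg RP2D, so the exposure that remains appears to be Part 2 and the reporting of the Part 1 MTD.

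**What to change.** 1. In Protocol 10.1.1, strike the eligibility condition so that evaluability for safety rests on at least one dose, as in 10.2.1 and SAP 5.2.
2. In Protocol 7.2 and 10.1.2, state for both Parts that ineligibility found after dosing, at any time and with or without withdrawal, does not remove an observed DLT from the count.
3. Reconcile SAP 5.4 with Protocol 7.2 and 3.1.4.1 and with the SAP 14.3.1 table list, so that one named DLT-evaluable population is used for the MTD and the DLT tables. PP can stay for response.

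The cost is one deleted phrase, one added rule and one SAP definition, carried in an amendment and a SAP revision. No dose, DLT criterion or stopping threshold changes, and no new data are needed.
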